## 5.3 DRUG CONCENTRATION MEASUREMENTS AND PHARMACOKINETICS

### 5.3.1 Assessment of pharmacokinetics

Blood [REDACTED] samples will be collected for the purpose of PK analysis. Further information about sampling is provided in section 5.3.2. Actual data and clock times of PK sampling will be recorded in CRF.

The planned PK analyses will require blood [REDACTED] samplings at the time points indicated in the [Flow Chart](#) and [Table 10.1: 1](#). Correct, complete and legible documentation of drug administrations and PK sampling times, as well as adequate handling and identification of PK samples, are mandatory to obtain data of adequate quality of the PK analysis.

### 5.3.2 Methods of sample collection

#### 5.3.2.1 Blood sampling for pharmacokinetic analysis

##### General aspects for all analytes

At a minimum, the sample tube labels should list BI trial number, patient number, visit, and planned sampling time. Further information such as matrix and analyte may also be provided.

Proprietary confidential information © 2020 Boehringer Ingelheim International GmbH or one or more of its affiliated companies

After completion of the trial, the plasma samples may be used for further methodological investigations (e.g., for stability testing or assessment of metabolites). However, only data related to the analyte and/or its metabolite(s) will be generated by these additional investigations. The trial samples will be discarded after completion of the additional investigations, but not later than 5 years after the clinical trial report (CTR) is archived.

**BI 3011441**

For quantification of drug in plasma, blood for each analyte will be drawn into a K2-EDTA (dipotassium ethylenediaminetetraacetic acid)-anticoagulant blood drawing tube at the times indicated in [Appendix 10.1](#).

Two plasma aliquots will be obtained and stored in an upright position at approximately -20°C or below at the trial site until shipment. Details on sample handling, processing and shipments are described in the lab manual.

**5.3.2.2 Urine sampling for pharmacokinetic analysis**

[REDACTED]

Details on sample handling, processing and shipments are described in the lab manual.

After completion of the trial, the urine samples may be used for further methodological investigations (e.g., for stability testing or assessment of metabolites). However, only data related to the analyte and/or its metabolite(s) will be generated by these additional investigations. The trial samples will be discarded after completion of the additional investigations but not later than 5 years after the CTR has been archived.

**5.4 ASSESSMENT OF BIOMARKER(S)**

**5.4.1 Methods of sample collection**

**5.5 BIOBANKING**

NA

**5.6 OTHER ASSESSMENTS**

NA

## **5.7 APPROPRIATENESS OF MEASUREMENTS**

All measurements performed during this trial are in accordance with measurements in Phase I oncology trials and will be performed in order to monitor safety aspects and to determine efficacy and PK [redacted] parameters in an appropriate way.

## 6. INVESTIGATIONAL PLAN

### 6.1 VISIT SCHEDULE

The visit schedule is in detail described in the [Flow Chart](#) for all patients enrolled into this trial. Unscheduled visits can be performed as necessary and assessments will be performed as required at the discretion of the Investigator.

### 6.2 DETAILS OF TRIAL PROCEDURES AT SELECTED VISITS

See the Flow Chart and [Section 5](#) for details on the procedures performed at each visit.

#### 6.2.1 Screening period(s)

##### Screening Period

All patients will need to sign the informed consent form (ICF). Only patients who have tested positive for activating NRAS/KRAS mutations by prior local analysis conducted in an international or country-specific certified laboratory (e.g. CAP/CLIA or ISO) are eligible for the trial. An archival tumour tissue sample will be submitted to the central laboratory to retrospectively confirm the NRAS/KRAS mutation status (see [Section 5.4](#)).

Demographic information (sex, year of birth, race) will be obtained, based on information in the patients' medical records.

Examinations and assessments per Flow Chart will be conducted and patients' medical history will be collected. Inclusion and exclusion criteria must be assessed (see [Sections 3.3.2](#) and [3.3.3](#)). Baseline images must be available as outlined in the Flow Chart.

Concomitant diagnoses and/or therapies present during trial participation (between first ICF and the first follow-up visit) will be recorded in the CRF. Medical history of the tumour disease will be obtained and reported in the CRF:

- The date of first histological diagnosis
- The primary tumour site
- The number and location of metastatic sites
- Previous treatment for the tumour disease, including any surgery, radiotherapy, and/or systemic therapy, including start and end dates and the outcome.

Examinations during the screening period also include electrocardiography, echocardiography, and an eye exam.

Re-screening will be allowed once for unexpected reason such as schedule conflict. Re-screened patients will receive a new patient number. In case of re-screening any procedures that fall outside the required screening window as defined in Flow Chart must be repeated.

A repeat testing during the screening period for items not meeting the eligibility criteria is basically not allowed.

## 6.2.2 Treatment period(s)

Treatment visits are specified in the [Flow Chart](#) and must be conducted as scheduled and outlined there. Treatment cycles are 4 weeks (28 days) in duration.

All planned visit dates are calculated from the start of Day 1 (Visit 1) of Cycle 1. If a patient misses a scheduled visit, and reports to the Investigator between the missed visit and the next scheduled visit, the assessments for the missed visit must be done with the actual date and the reason must be given for the delayed visit. All subsequent visits must adhere to the scheduled programme of visits for all cycles of treatment. Hospitalisation for administrative reasons (e.g. for the first days of Cycle 1) will not be considered as SAE. PK blood sampling timepoints are outlined in [Appendix 10.1](#) and biomarker sampling is detailed in [Section 5.4](#).

**Imaging visits must adhere to the schedule provided in the Flow Chart at all times, unless they are scheduled for suspected progressive disease.**

## 6.2.3 Follow-up period and trial completion

### 6.2.3.1 End of treatment visit and EOR

The EOT visit will be performed as soon as possible (within 7 days) after permanent discontinuation of all trial medications for any reason or as soon as possible after the Investigator became aware that the trial medication had been terminated. The assessments of the EOT visit will then be performed instead at the next planned visit. If the patient finishes active treatment without having progressive disease, tumour assessment/imaging must be performed at the time of treatment discontinuation, unless it has been done within the past 4 weeks.

The EOR will be performed 30 (+7) days after permanent discontinuation of all trial medications and is primarily to collect follow-up safety information as required by regulatory authorities. For the majority of patients, progression will already be documented at this point.

### 6.2.3.2 Extended follow-up period

For patients who did not discontinue treatment due to progressive disease, additional follow-up visits after the 30-day safety follow-up visit will be performed every 8 weeks to continue tumour imaging until progressive disease or another withdrawal criterion is met.

The follow-up for progression period will end at the time that one of the following events is met:

- Disease progression based on RECIST 1.1
- Start of a new anti-cancer therapy
- Lost to follow-up
- Death
- End of whole trial as specified in [Section 8.6](#).

The following will be obtained and/or performed during the follow-up visits for progression.

- For each reportable SAE/AESI, the Investigator should provide the information with regard to concomitant medication and the medication administered to treat the AE on the

Proprietary confidential information © 2020 Boehringer Ingelheim International GmbH or one or more of its affiliated companies

appropriate CRF pages and the SAE form including trade name, indication and dates of administration

- Perform physical examination
- Record performance score/status (e.g., ECOG)
- Perform tumour assessment and imaging
- Treatment and date with any subsequent anti-cancer drug / therapy including the name and type of the anti-cancer drug and/or best supportive care (if applicable)
- Outcome (date of and reason for death [if applicable], in case the patient had progressive disease the actual date of progressive disease shall be recorded).

#### **6.2.3.3 Trial completion for an individual patient**

A patient is considered to have completed the trial in case any of the following applies:

- Completion of planned follow-up period
- Lost to follow-up
- Refusal to be followed-up
- Death.

## 7. STATISTICAL METHODS AND DETERMINATION OF SAMPLE SIZE

### 7.1 STATISTICAL DESIGN – MODEL

The trial will be performed as an open-label trial. The objective of the design is to determine the MTD defined as the highest dose with less than 25% risk of the true DLT rate being equal or above 0.33 (EWOC criterion). The phase I dose-finding will be guided by a Bayesian 2-parameter logistic regression model with overdose control ([R13-4806](#); [R13-4803](#)).

The model is given as follows:

$$\text{logit}(\pi_d) = \log(\alpha) + \beta * \log(d/d^*),$$

where  $\text{logit}(\pi) = \log(\pi/(1-\pi))$ .

$\pi_d$  represents the probability of having a DLT in the MTD evaluation period at dose  $d$ ,  $d^* = 8$  mg is the reference dose, allowing for the interpretation of  $\alpha$  as the odds of a DLT at dose  $d^*$ , and  $\theta = (\log(\alpha), \log(\beta))$  with  $\alpha, \beta > 0$  is the parameter vector of the model. The estimated probability of a DLT at each dose level from the model will be summarized using the following intervals:

Under toxicity: [0.00, 0.16)

Targeted toxicity: [0.16, 0.33)

Over toxicity: [0.33, 1.00]

The BLRM-recommended dose for the next cohort is the level with the highest posterior probability of the DLT rate falling in the target interval [0.16, 0.33) among the doses fulfilling EWOC. Applying the EWOC criterion, it should be unlikely (<25% posterior probability) that the DLT rate at that dose will exceed 0.33. However, the maximum allowable dose increment for the subsequent cohort will be no more than 50 % for each dose level.

The MTD may be considered reached if one of the following criteria is fulfilled:

1. The posterior probability of the true DLT rate in the target interval [0.16 – 0.33) of the MTD is above 0.5, OR
2. At least 12 patients have been treated in the dose escalation phase of the trial, of which at least 6 at the MTD.

The SMC may recommend stopping the dose escalation phase after the criterion for MTD is fulfilled. Further patients may be included to confirm this MTD estimate. If no DLT is observed at a dose of which the efficacy is considered sufficient, the SMC may decide to include an additional number of patients at this dose level and to declare this dose as the dose recommended for further testing

Since a Bayesian approach is applied, a prior distribution  $f(\theta)$  for the unknown parameter vector  $\theta$  needs to be specified.

This prior distribution will be specified as a mixture of three multivariate normal distributions, i.e.

$$a(\theta) = a_1 f_1(\theta) + a_2 f_2(\theta) + a_3 f_3(\theta)$$

with

$a_i, i = 1, 2, 3$  the prior mixture weights ( $a_1 + a_2 + a_3 = 1$ )

and

$f_i(\theta) = MVN(\mu_i, \Sigma_i)$

the multivariate normal distribution of the  $i$ -th component with mean vector  $\mu_i$  and covariance matrix  $\Sigma_i$ , where

$$\Sigma_i = \begin{pmatrix} \sigma_{i,11}^2 & \sigma_{i,11}\sigma_{i,22}\rho_i \\ \sigma_{i,11}\sigma_{i,22}\rho_i & \sigma_{i,22}^2 \end{pmatrix}$$

Mixture prior distributions have the advantage that they allow for specification of different logistic dose-toxicity curves, therefore making the prior more robust.

Prior derivation:

For the current trial, relevant information in the form of human data was available. Therefore, the three mixture components were established as follows:

1. The MAP prior using the historical data for LPN3794, modified to include grade 2 retinopathy as DLT, can be found in Table 7.1:1

Table 7.1:1 Historical data for LPN3794 (modified to include grade 2 retinopathy as DLT)

Trial	Dose (mg)	N of patients with DLTs during MTD evaluation period / N of patients
LPN3794 (including grade 2 retinopathy as DLT)	2	0/1
(including grade 2 retinopathy as DLT)	4	0/1
	6	0/3
	8	3/9
	10	2/5
	16	1/1

This yields  $\mu_1 = (-0.94, 0.61)$ . The standard deviations were set such that large uncertainty about the parameter means is reflected, and the correlation was set to 0, thus yielding  $\sigma_{1,11} = 0.91$ ,  $\sigma_{1,22} = 0.91$  and  $\rho_1 = -0.08$ , respectively. The prior weight  $a_1$  for the first component was chosen as 0.8.

2. A high-toxicity weakly informative prior was derived reflecting the case that the compound would be much more toxic than expected. For this prior component, it was assumed that the median DLT rate at 2 mg would equal 0.10, and the median DLT at the anticipated MTD of 8 mg would equal 0.70. These assumptions yield  $\mu_2 = (0.85, 0.79)$ . The standard deviations and correlations were set identical to the weakly informative prior, i.e.  $\sigma_{2,11} = 2$ ,  $\sigma_{2,22} = 1$  and  $\rho_2 = 0$ , respectively. The prior weight  $a_2$  for the second component was chosen as 0.1.

3. A low-toxicity weakly informative prior was derived reflecting the case that the compound would be much less toxic than expected. For this prior component, it was assumed that the median DLT rate at 2 mg would equal 0.005, and the median DLT at the anticipated MTD of 8 mg would equal 0.1. These assumptions yield  $\mu_3 = (-2.20, 0.80)$ , i.e. basically a flat curve. The standard deviations and correlations were set to  $\sigma_{3,11} = 2$ ,  $\sigma_{3,22} = 1$ . The correlation was set to 0, i.e.  $\rho_3 = 0$ . The prior weight  $a_3$  for the third component was chosen as 0.1.

A summary of the prior distribution is provided in Table 7.1:2. Additionally, the prior probabilities of DLTs at different doses, as well as the corresponding probability of under-, targeted and over toxicity, are shown in Table 7.1:3. Graphically, the prior medians with accompanying 95% credible intervals are shown in [Figure 7.1:1](#). As can be seen from both, the table and the figure, the prior medians of the DLT probabilities are in-line with the prior medians derived from the weakly informative prior, and the uncertainty around the medians is large, showing the low amount of information this prior provides. This is also supported by the prior sample size, i.e. the information contained in the prior. This is approximately equal to 2.8 patients at 4 mg. A detailed evaluation of the model using hypothetical data scenarios and operating characteristics is provided in the statistical [Appendix 10.2](#).

Table 7.1:2 Summary of prior distribution

[figure not shown]
Prior Component	Mixture Weight	Mean Vector	SD Vector	Correlation
1: MAP prior	0.800	(-0.94, 0.61)	(0.91,0.91)	-0.08
2: High Tox.	0.100	(0.85,0.79)	(2,1)	0
3: Low Tox.	0.100	(-2.20,0.80)	(2,1)	0

Table 7.1:3 Prior probabilities of DLTs at selected doses

Dose	Probability of true DLT rate in			Quantiles				
	[0-0.16)	[0.16-0.33)	[0.33-1)	Mean	SD	2.5%	50%	97.5%
4 mg	0.682	0.189	0.128	0.147	0.182	0.000	0.081	0.688
6 mg	0.492	0.274	0.233	0.224	0.205	0.003	0.164	0.804
7 mg	0.370	0.320	0.310	0.272	0.213	0.012	0.218	0.853
8 mg	0.248	0.330	0.422	0.329	0.220	0.024	0.285	0.897

Figure 7.1:1

Prior medians and 95% credible intervals

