### 3. DESCRIPTION OF DESIGN AND TRIAL POPULATION

#### 3.1 OVERALL TRIAL DESIGN

The trial is an open-label, non-randomised phase I trial of BI 3011441 as monotherapy to investigate the safety/tolerability, PD and PK profile at selected dose levels in Japanese patients with NRAS/KRAS mutation positive advanced or metastatic refractory solid tumours. Patients will be enrolled based on the available NRAS/KRAS mutation status previously identified by local test results performed prior to screening. The data obtained from the trial will determine the MTD estimate based on a Bayesian logistic regression model with overdose control ([R13-4803](#)). The BLRM estimates the MTD by updating estimates of the probability of observing a DLT in the MTD evaluation period for each dose level in the trial as patient information becomes available. At any time in the trial, it will not be permitted to escalate to a dose which does not fulfil the escalation with overdose control (EWOC) principle (refer to [Section 7](#)).

The provisional dose levels to be evaluated will be 4mg, 6mg and 8mg, which includes the previously established MTD of 8mg for Caucasian patients. For any dose-escalation cohort, at least 3 patients will be required (refer to Section 7). However, in the case that only 2 patients are evaluable and neither has experienced a DLT within the MTD evaluation period, then dose-escalation can occur based on these 2 patients. For determination of MTD or RD, 6 patients will be enrolled at least. A BLRM with overdose control will be performed once the enrolment of 3 patients at each dose level has been completed and these patients completed the first cycle of treatment of BI 3011441. Each cycle will consist of 28 days (4 weeks) and patients will continue the treatment until undue drug toxicity, disease progression, or withdrawal of consent, whichever occurs first. The longest treatment period will be 2 years if deemed safe and efficacious. Intra-patient dose escalation will be allowed if there is an indication from higher-dose cohorts that there is a positive-risk-benefit once the patient completed the 1st cycle of treatment including PK sampling.

[figure not shown]

Figure 3.1: 1

Study design

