## 7.6 DETERMINATION OF SAMPLE SIZE

No formal statistical power calculations to determine sample size were performed for these parts of the trial. Approximately 12 patients (including at least 6 patients at MTD) are expected for dose escalation based on the number of dose levels/cohorts that are tested. Fewer or more patients might be needed based on the recommendation of the SMC. However, the actual number of patients will depend on the number of dose cohorts tested. Detailed information of simulation study to evaluate operating characteristics of the BLRM will be provided in [section 10.2](#).

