### Hypothetical data scenarios

Hypothetical data scenarios are shown in Table 10.2:1. These scenarios reflect potential on-study data constellations and related escalation as allowed by the model. It is assumed that each cohort has exactly three patients who are all evaluable. For each scenario, the probability of overdose for the current dose, as well as the next potential dose and related probabilities of under-dosing, target dose, and over-dosing are shown.

For example, scenario 1 represents the case that no DLT is observed in the first three patients at the starting dose of 4 mg. In this case, the next optimal dose, i.e. the dose with the highest probability of being in the target interval, is 7 mg. Since the escalation is restricted to a maximum of 50 % from the previous dose per protocol, the next dose to be tested in the trial would be 6 mg.

Scenario 4 is the case that one DLT is observed in the first three patient at the starting dose of 4mg and no DLT is observed in second three patient at 4mg; in this case the model recommend to escalate 6 mg . Scenario 5 is the case that one DLT is observed in the first three patient at the starting dose of 4 mg and one DLT is observed in second three patient at 4 mg; in this case the model recommend to 4 mg. Scenario 6 represents the case that 3 patients have been treated at 4 mg and 3 patients at 6 mg, none of them with a DLT. In this case, the model recommends to escalate to 8 mg.

Scenarios 16 to 22 are the cases where doses of 4 mg and 6 mg have been completed with no DLT and the BLRM recommends 8mg to be tested next. More specifically, scenarios 18, 21 and 22 are the cases that dose of 8 mg have been completed and BLRM recommend to reduce to 7mg. Scenario 19, 20 illustrate a case where escalation has proceeded up to the highest dose of 8 mg, where the MTD could be declared at 8 mg.

Scenarios 23 to 26 are the cases that 1 DLT out of 6 patients in 4mg cohort and no DLT in 3 patients in 6 mg cohort, BLRM recommends 7 mg to be tested next. In scenarios 23, the next optimal dose, i.e. the dose with the highest probability of being in the target interval, is 8 mg. In such cases, SMC will suggest whether to open up 8mg cohort or keep treating patients at 7mg. In scenarios 25, the next optimal dose, i.e. the dose with the highest probability of being in the target interval, is 8 mg. In such cases, SMC will suggest whether to open up 8 mg

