7.4 PRIMARY ENDPOINT

7.4.1 Primary analysis of the primary endpoint

For the determination of the MTD, only evaluable patients for MTD in the dose escalation part will be considered (i.e., the MTD set). In this section of the report the data that led to the determination of the MTD are documented and summarised. To be specific, an overall summary of the number of patients with DLTs during the MTD evaluation period (i.e., the first treatment cycle) will be provided for each dose cohort.

The dose escalation and determination of MTD is guided by the BLRM with overdose control specified in CTP Section 7 based on the DLT data in the MTD set. Specifically, estimation of the MTD will be based on the estimation of the posterior probability of the incidence of DLT in toxicity categories during the MTD evaluation period for all evaluable patients for MTD. Tables and bar charts displaying the posterior probabilities of the true DLT rates being in either the under-toxicity interval, the target-toxicity interval or the over-toxicity interval will be produced.

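### MTD criterion 1 in Protocol 7.1 has no minimum number at the dose, although 7.6 expects at least 6 there, and Table 10.2:3 does not come from the 7.1 criteria as written

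*Protocol*

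**What the plan says.** Protocol 7.1 introduces the rule with "The MTD may be considered reached if one of the following criteria is fulfilled". Criterion 1 is that the posterior probability of the target interval [0.16, 0.33) "of the MTD is above 0.5, OR". Criterion 2 is "At least 12 patients have been treated in the dose escalation phase of the trial, of which at least 6 at the MTD". Either is enough. The same section adds "Further patients may be included to confirm this MTD estimate" and leaves the decision to stop with the SMC.

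Two other protocol sections give numbers. Section 3.1: "For determination of MTD or RD, 6 patients will be enrolled at least", with no dose named. Section 7.6: "Approximately 12 patients (including at least 6 patients at MTD) are expected for dose escalation".

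The SAP adds no minimum. Its section 7.4.1 says "The dose escalation and determination of MTD is guided by the BLRM with overdose control specified in CTP Section 7", and its section 5.1 says that the SMC determines the MTD.

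Protocol 10.2 describes the simulation as 1000 trials per scenario in cohorts of 3. It gives neither the rule that ended a simulated trial nor a cap on patient numbers.

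**The concern.** The MTD is a primary endpoint. Read literally, 7.1 lets it be considered reached at a dose where only 3 patients were treated, which is not what 7.6 expects.

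Table 10.2:3 is the only evidence on how the design performs, and 10.2 uses it to call the model conservative. If the table came from a rule other than the one in 7.1, its selection rates and patient numbers do not describe the trial as written. A reader cannot tell which rule they do describe.

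**Working it through.** *Numbering.* Data scenarios are the 46 rows of Table 10.2:1. Scenarios 1 to 6 are the assumed truths of Table 10.2:2.

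**1. Can criterion 1 be met on 3 patients?** From intact rows of Table 10.2:1, each with 3 patients at 8 mg:

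| Data scenario | DLTs at 8 mg | P(target) | P(overdose) |
|---|---|---|---|
| 33 | 1/3 | 0.563 | 0.178 |
| 38 | 1/3 | 0.597 | 0.226 |
| 43 | 1/3 | 0.560 | 0.200 |

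All three exceed 0.5 with overdose probability below 0.25. All fail criterion 2, because only 3 patients are at the dose.

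Data scenario 33 can be reached without either criterion having been met earlier. Printed P(target) at the recommended dose is 0.365 (data scenario 2), 0.459 (4), 0.474 (12) and 0.484 (23) on the way.

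**2. Hand check of Table 10.2:3.** Take 0/3 at 4 mg, 0/3 at 6 mg, then 0/6 at 8 mg. Data scenarios 1, 6 and 16 give the recommendations along this path. It ends at data scenario 19 with N = 12 and 6 at the dose, so criterion 2 is met. The narrative describes data scenarios 19 and 20 as a case "where the MTD could be declared at 8 mg". The path's probability under the true rates of Table 10.2:2 is:

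- Scenario 3: 0.96³ × 0.89³ × 0.84⁶ = 0.885 × 0.705 × 0.351 = 21.9%, about 219 of 1000 trials
- Scenario 4: 0.90³ × 0.80³ × 0.70⁶ = 4.4%
- Scenario 1: 0.853³ × 0.776³ × 0.671⁶ = 2.6%
- Scenario 5: 0.96³ × 0.80³ × 0.55⁶ = 1.3%

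The printed minimum number of DLTs is 1 in each of these scenarios.

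**3. Full recomputation.** Inputs:

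- Model (7.1): logit(π_d) = log α + β log(d/8), with the three-component prior of Table 7.1:2
- Dose rule (7.1): highest P(target) among doses with P(π ≥ 0.33) < 0.25, and at most a 50% step
- Start at 4 mg (4.1.2), cohorts of 3, truths from Table 10.2:2 (with the added 2 mg level in Scenario 6)

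The posterior was computed on a grid. It reproduces Table 7.1:3 and the rows of Table 10.2:1 that were recomputed to within about 0.02. Two states sit at the overdose limit: 2/6 at 4 mg (0.249 printed and recomputed) and data scenario 13 (0.243 printed, 0.259 recomputed). Ranges below cover both decisions for each. All paths were then enumerated with exact probabilities under two readings of 7.1:

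- R1: stop when a criterion is met at the recommended dose
- R2: stop only if that dose is also the one just treated

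Mean number of patients:

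| | Sc. 1 | Sc. 2 | Sc. 3 | Sc. 4 | Sc. 5 |
|---|---|---|---|---|---|
| Printed | 15.3 | 11.6 | 16.8 | 13.6 | 15.9 |
| R1, as written | 11.8 | 10.3 | 13.0 | 12.4 | 12.8 |
| R2, as written | 13.0 | 11.2 | 13.6 | 13.6 | 14.2 |
| R1 with at least 6 at the dose | 13.5 | 11.4 | 14.1 | 14.2 | 14.7 |
| R2 with at least 6 at the dose | 14.2 | 11.9 | 14.6 | 14.9 | 15.6 |

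The sampling error of a 1000-trial mean is 0.07 to 0.18. R2 agrees in Scenario 4 but falls short by 2.3, 3.2 and 1.7 patients in Scenarios 1, 3 and 5. Scenario 6 does not discriminate: 8.7 to 8.9 in all four forms, 8.6 printed.

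Maximum N under R1 is 21 in Scenarios 1 to 5, against 30 to 42 printed. Under R2 it can exceed 30, but N of 42 in Scenario 3 is expected in fewer than 0.01 of 1000 trials.

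Overdose selection, with sampling error √(0.322 × 0.678/1000) = 1.5 points:

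| | Printed | R1 | R2 |
|---|---|---|---|
| Scenario 2 | 32.2% | 42.0% (38.3–46.4) | 37.4% (35.1–43.1) |
| Scenario 5 | 35.1% | 44.6% | 41.0% (39.8–41.0) |

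If a trial stops as soon as a criterion is met, declared MTDs with fewer than 6 at the dose make up 22–40% under R1 and 17–26% under R2.

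**4. Does a minimum of 6 recover the table?** Not as a whole. R1 with the minimum gives under/target/over/stopped of 19.2/66.8/0/14.0 in Scenario 1 (printed 19.4/66.3/0/14.3), and it also agrees in Scenarios 3 and 6. It is off in Scenario 2 (0/31.0/35.7/33.3 v 0/25.2/32.2/42.6) and Scenario 4 (14.2/79.4/0/6.4 v 11.7/76.7/0/11.6). In Scenario 5 its target share is 52.6% against 48.7%. The patient and DLT columns are not reproduced.

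Adding an unstated condition of at least one DLT to R2 with the minimum brings Scenario 3 to 16.2 patients. Scenario 1 is then still 14.3 (printed 15.3) and Scenario 4 is 15.1 (printed 13.6).

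**The case against.** The rule is permissive. Nothing obliges the SMC to stop at 3 patients, confirmatory patients are allowed, and the sentence in 3.1 can plausibly be read as 6 at that dose. This stands: the 7.1 point is a wording gap that needs reconciling.

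A reader might infer that the authors used a hidden minimum of 6, because data scenarios 24 and 28 meet criterion 1 and are not called an MTD. The documents do not support this. Every example linked to an MTD (19, 20, 25, 26, 30, 31) also meets criterion 2, using counts inferred from the printed posteriors where rows are broken. The narrative is equally silent on 9, 35, 36, 40, 41, 45 and 46, which meet criterion 1 with 6 at the dose. The partial agreement in step 4 does not show that a minimum was simulated either.

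A reader might also infer that an MTD can be declared where nobody was treated, from data scenario 14 (7 mg, P(target) 0.553). That holds only under R1. Under R2 it cannot happen, and no text declares 7 mg the MTD there.

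Finally, the sampling errors ignore differences between the sponsor's R/JAGS runs and a grid, as well as the two boundary decisions. That is fair, and it weakens the R2 overdose comparison in Scenario 2, whose lower end of 35.1% is only about 2 standard errors from the printed figure. It does not explain the 3-patient gap in Scenario 3. The hand check uses only the printed recommendations and assumed truths.

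**Conclusion.** The point holds in two parts.

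First, criterion 1 allows the MTD to be considered reached with 3 patients at the dose, while 7.6 expects at least 6 and 3.1 leaves the dose open. The worked examples do not settle whether a minimum was intended.

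Second, Table 10.2:3 does not come from the 7.1 criteria as written, under either reading. In Scenarios 1, 3 and 5 mean patient numbers are 1.7 to 3.8 below the printed values. The central overdose-selection figures are 5 to 10 points above the printed ones in Scenarios 2 and 5, so the table shows the written rule as safer than it is. About 22% of Scenario 3 trials would end without a DLT, where the table shows a minimum of 1.

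This rests on the printed prior and true rates, fully evaluable cohorts of 3, and trials that stop when a criterion is met. No variant tried reproduces the whole table, so the simulated rule has to be stated by the sponsor; it cannot be inferred. This should be corrected, but it does not by itself invalidate the design.

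**What to change.** Reconcile criterion 1 in 7.1 with 7.6 and 3.1, in one of two ways:

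- add to criterion 1 *and at least 6 evaluable patients have been treated at that dose*; or
- state in 7.6 and 3.1 that criterion 1 stands without a minimum.

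In 10.2, state the exact stopping rule simulated, including any condition on DLTs or on staying at the same dose, any cap on N, and how the added 2 mg level in Scenario 6 was treated. Rerun Table 10.2:3 under the final 7.1 rule. Restate the selection rates and the expected and maximum patient numbers in 7.6 and 10.2 from that run.

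The cost is protocol wording and one simulation run. The first option adds 1.0 to 1.9 patients on average under R1, or 0.7 to 1.4 under R2, in Scenarios 1 to 5; 7.6 already expects 6 at the MTD.
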